8.5.2.8 Concizumab ELISA

Concizumab ELISA will be performed at all visits except at screening and at visit 3. Samples will be collected pre-dose at visit 2, 9 and 16. For the unscheduled 24 hour PK visit, samples are collected; 1 hour pre-dose (-1hour), 1(±10 min.), 3(±10 min.), 6(±10 min.), 9(±10 min.), 12(±20 min.) and 24 hour(s) (±20 min.) post dose, related to the daily dosing of concizumab.

Concizumab will be quantified using a validated ELISA assay. Recombinant human TFPI will be used to capture concizumab. A colorimetric detection signal is obtained by the enzymatic reaction of horseradish peroxidase labelled anti-human IgG4 specific antibodies with the chromogenic

Protocol
Trial ID:NN7415-4255
UTN:U1111-1179-3872
EudraCT no.:2016-000614-29

~~CONFIDENTIAL~~

Date: 28 August 2018
Version: 5.0
Status: Final
Page: 70 of 127

Novo Nordisk

substrate TMB (3,3',5,5'-tetramethylbenzidine). The amount of anti-TFPI present in the calibration, quality control and test samples correlates with the obtained signal strength.

Validation of the assay follows current guidelines for bioanalytical method validation. Bioanalytical data will be reported in a bioanalytical report.

8.5.2.9 Total TFPI

Total TFPI ELISA sampling will be performed at all visits except at visit 3. Samples will be collected pre-dose at visit 2, 9 and 16.

The Total TFPI ELISA is included as an exploratory PD assessment.

The total TFPI level (free and concizumab bound) will be included as an exploratory biomarker assessment. The assay is an ELISA, where TFPI is captured by polyclonal anti-TFPI antibody, distanced from the binding site of concizumab, meaning that both free TFPI and concizumab bound TFPI will be captured. Detection will be obtained with a monoclonal antibody against TFPI, which does not bind to the concizumab epitope. Data will be reported in ng/mL TFPI. Total TFPI ELISA will be performed at all visits, except visit 3. Sample will be collected pre-dose at visit 2.

8.5.3 Human biosamples

If patient permission is obtained, plasma, serum and/or DNA for genotyping samples are to be taken for long term retention. The blood samples can be stored up to 15 years, for future potential exploratory purposes please refer to section [24.2](#).

Antibody samples storage and retention see section [24.2.1](#). The investigator is not able to review the results of antibody measurements in relation to AEs as these are analysed after LPLV.

If applicable, samples will be collected at visit 1 and at visit 17.

8.6 Other assessments

8.6.1 Patient reported outcomes

In this trial a newly developed disease specific PRO - the Hemophilia Treatment Experience Measure (Hemo-TEM) - is being validated. In order to assess the psychometric properties of Hemo-TEM, other questionnaires will be provided; see further [appendix 1](#).

The following ePRO questionnaires are used:

- Haemophilia Treatment Experience Measure (Hemo-TEM)

Protocol
 Trial ID:NN7415-4255
 UTN:U1111-1179-3872
 EudraCT no.:2016-000614-29

CONFIDENTIAL

Date: 28 August 2018
 Version: 5.0
 Status: Final
 Page: 71 of 127

Novo Nordisk

- Validated Hemophilia Regimen Treatment Adherence Scale – Prophylaxis (VERITAS-Pro[®])/Validated Hemophilia Regimen Treatment Scale (/ VERITAS-PRN[®])¹⁴
- 36-Item Short Form Health Survey (SF-36v2) (4 week recall)¹⁵
- Patient Global Impression of Change (PGI-C)
- Sheehan Disability Scale (SDS)¹⁶
- Treatment Satisfaction Questionnaire for Medication (TSQM, version II)¹⁷⁻¹⁹
- Haemophilia - Device Assessment Tool (H-DAT)
- Injection Site Reaction Questionnaire (ISRQ) domain of SIAQ (SIAQ-ISRQ)²⁰

The PROs should be assessed at the scheduled visits following the order listed below:

- visit 1 (Hemo-TEM, VERITAS-Pro[®] or VERITAS-PRN[®])
- visit 2 (Hemo-TEM, SF-36v2, SDS, TSQM, SIAQ-ISRQ)
- visit 4 (PGI-C, Hemo-TEM)^a
- visit 5 (PGI-C, Hemo-TEM)
- visit 6 (PGI-C, Hemo-TEM)
- visit 7 (PGI-C, Hemo-TEM)
- visit 8 (PGI-C, Hemo-TEM)
- visit 9 (PGI-C, Hemo-TEM, SF-36v2, SDS, TSQM, H-DAT, SIAQ-ISRQ)
- visit 10 (Hemo-TEM, SF-36v2, SDS, TSQM, SIAQ-ISRQ)
- visit 15.1 or 16 (Hemo-TEM, SF-36v2, SDS, TSQM, H-DAT, SIAQ-ISRQ)

At visit 1 before any visit-related activities all patients should complete Hemo-TEM and VERITAS-Pro[®] (if the patient at baseline receives prophylactic treatment) / VERITAS-PRN[®] (if patient at baseline receives on demand treatment).

At visit 2 before any visit-related activities all patients should complete Hemo-TEM, SF36v2, SDS, TSQM and SIAQ-ISRQ.

At visit 4-8: before any visit-related activities the patient should complete the PGI-C before the Hemo-TEM. These are the rules that apply:

- If the patient responds “1” to question 1 in the PGI-C, the patient should also complete the Hemo-TEM. In this case the patient should not fill in the PGI-C any more in the trial and the Hemo-TEM only again at visit 9.
- If the patient responds “0” or “2” to question 1 in the PGI-C, the patient should not complete any other questionnaires at this visit, but should repeat the procedure at next visit.

At visit 9 if the patient has responded “0” or “2” in the PGIC at all previous visits, the patient should complete PGI-C. All patients should complete Hemo-TEM, SF-36v2, SDS, TSQM, H-DAT and SIAQ-ISRQ.

Protocol
Trial ID:NN7415-4255
UTN:U1111-1179-3872
EudraCT no.:2016-000614-29

~~CONFIDENTIAL~~

Date: 28 August 2018
Version: 5.0
Status: Final
Page: 72 of 127

Novo Nordisk

At visit 10 all patients should complete Hemo-TEM, SF-36v2, SDS, TSQM and SIAQ-ISRQ.

At visit 15.1 or 16 all patients should complete Hemo-TEM, SF-36v2, SDS, TSQM, H-DAT and SIAQ-ISRQ. The investigator must check the ePROs for completeness.

The completed ePROs should be transmitted to the ePRO database by the investigator at each visit.

All PROs can be found in [Appendix I](#).

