o	The trial patient must be in a non-bleeding state at the time of the first trial product administration (TPA), and should not have received any haemostatic drug (e.g. FVIII) for prophylaxis or treatment of a bleeding episode within a period of 48 hours prior to first TPA.
p	Patient should be dose escalated at next scheduled visit if he experiences ≥ 3 spontaneous bleeding episodes within the preceding 12 weeks of treatment with concizumab. If investigator judges that next scheduled visit is too late an unscheduled visit should be performed for dose escalation.
q	Home treatment training must take place at visit 2 at the latest and whenever needed afterwards. Home treatment training comprises handing out of Direction for Use (DFU), training in administration of concizumab with NovoPen [®] 4, turoctocog alfa and data entry in eDiary. Further the patients will be trained in recognition of signs/symptoms of thrombosis.
r	In case patients are participating in the 24 hour PK-session the sampling time points for thrombin generation, concizumab ELISA and Free TFPI are: pre-dose (-1 hour), 1h (\pm 10 min), 3h (\pm 10 min), 6h (\pm 10 min), 9h (\pm 10 min), 12h (\pm 20 min) and 24h (\pm 20 min). All time points, except pre-dose, occur after concizumab administration
s	Visit repeated every 8 week until patient either discontinues, completes extension or is enrolled into a subsequent trial with concizumab
t	For patients continuing a subsequent trial End of Trial must be completed at visit 16. For patients declining participation in a subsequent trial the End of Trial must be completed at visit 17, 8 weeks after End of Treatment.
u	PRO questionnaires should only be completed at 15.1 for patients continuing in the prolongation of the trial.
v	PRO questionnaires should only be completed at visit 16 for patients not continuing in the prolongation of the trial

Protocol
 Trial ID:NN7415-4255
 UTN:U1111-1179-3872
 EudraCT no.:2016-000614-29

~~CONFIDENTIAL~~

Date:	28 August 2018	Novo Nordisk
Version:	5.0	
Status:	Final	
Page:	21 of 127	

3 Background information and rationale for the trial

The trial will be conducted in compliance with this protocol, International Conference on Harmonisation Good Clinical Practice (ICH GCP)¹ and applicable regulatory requirements, and in accordance with the Declaration of Helsinki² and ISO 14155³.

In this document, the term investigator refers to the individual responsible for the overall conduct of the clinical trial at a trial site.

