8.1.10 Extension Part

8.1.10.1 Visit 10 (Assessment visits)

Visit 10 is to be scheduled on trial day 225 (32 weeks) , with a visit window of ± 7 days.

Assessments are to be performed according to the flowchart section [2](#) and the assessment results from concomitant medication, vital signs, Body measurements (weight only) and details of adverse events must be entered into the eCRF.

Patients will be asked to complete the ePRO questionnaires before any other trial related activities are performed according to section [8.6.1](#);

- Hemo-TEM
- SF-36v2
- SDS
- TSQM
- SIAQ-ISRQ

Investigator is to perform compliance check of treatment and reporting of bleeding episodes through reviewing collected data from the eDiary. Based on the assessment of any spontaneous bleeding episodes the investigator must evaluate if an escalation of the concizumab doses is needed according the escalation rules described in section [5.3.1](#). All decisions to escalate the concizumab dose must be recorded in the eCRF.

In order to determine the correct amount of the patient's daily dose of concizumab, until next scheduled visit, investigator will consult the dosing-table in the TMM on basis of the patient's current body weight. Investigator will communicate any corrections in the daily dose of concizumab to the patient and record the dose for the coming home treatment period in the eCRF.

A dispensing call must be performed in the IWRS.

At the visit the patient will be provided with trial product (concizumab and if necessary rFVIII (turoctocog alfa)) and injection kits to be able to conduct home treatment until next scheduled visit.

Protocol
 Trial ID:NN7415-4255
 UTN:U1111-1179-3872
 EudraCT no.:2016-000614-29

~~CONFIDENTIAL~~

Date: 28 August 2018
 Version: 5.0
 Status: Final
 Page: 50 of 127

Novo Nordisk

The patient will be asked to return all used, partly used and unused concizumab cartridges and turoctocog alfa (FVIII) during the trial as instructed by the investigator. Drug accountability must be performed at all visits for concizumab and rFVIII (turoctocog alfa) including injection kits, if applicable. Unused sodium chloride syringes should be returned to site at every visit and new sodium chloride syringes should be dispensed to the patient.

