8.1.10.2 Visit 11, 12, 13, 14 and 15, 15.1, 15.2, 15.n (Assessment visits)

Visits 11 to 15.n are to be scheduled with an interval of 8 weeks with a visit window of \pm 7days until the patient either discontinues treatment or completes visit 16.

If the patient declines participation in the prolongation of the extension, visit 16 should be conducted 4 weeks after visit 15 (see Section [8.1.10.3](#))

Assessments are to be performed according to Table [Table 2–1](#) and the assessment results from physical examination (applicable for V12), concomitant medication, vital signs, Body measurements (weight only) and details of adverse events must be entered into the eCRF.

Investigator is to perform compliance check of treatment and reporting of bleeding episodes through reviewing collected data from the eDiary. Based on the assessment of any spontaneous bleeding episodes the investigator must evaluate if an escalation of the concizumab doses is needed according the escalation rules described in section [5.3.1](#). All decisions to escalate the concizumab dose must be recorded in the eCRF.

The patient will be asked to return all used, partly used and unused concizumab cartridges and turoctocog alfa (FVIII) during the trial as instructed by the investigator. Drug accountability must be performed at all visits for concizumab and rFVIII (turoctocog alfa) including injection kits, if applicable. Unused sodium chloride syringes should be returned to site at every visit and new sodium chloride syringes should be dispensed to the patient.

In order to determine the correct amount of the patient's daily dose of concizumab, until next scheduled visit, investigator will consult the dosing-table in the TMM on basis of the patient's current body weight. Investigator will communicate any corrections in the daily dose of concizumab to the patient and record the dose for the coming home treatment period in the eCRF.

A dispensing call must be performed in the IWRS.

At the visit the patient will be provided with trial product (concizumab and if necessary rFVIII (turoctocog alfa)) and injection kits to be able to conduct home treatment until next scheduled visit.

At visit 15.1 only patients continuing in the prolongation will be asked to complete the PRO questionnaires before any other trial related activities are performed according to section [8.6.1](#);

Protocol
 Trial ID:NN7415-4255
 UTN:U1111-1179-3872
 EudraCT no.:2016-000614-29

~~CONFIDENTIAL~~

Date: 28 August 2018

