8.1.10.3 Visit 16 (Assessment visit end of treatment with Concizumab) - Extension part

Visit 16 is to be scheduled:

- on trial day 533 (for patients declining participation in the prolongation of the trial)
- or later (for patients continuing in the extension or enrolled in a subsequent trial)

with a visit window of ± 7 days.

Visit 16 should be scheduled to be conducted at the last day of treatment with concizumab.

Treatment with concizumab must take place after the blood sampling at this visit.

Patients **not** continuing in the prolongation will be asked to complete the PRO questionnaires before any other trial related activities are performed according to section [8.6.1](#);

- Hemo-TEM
- SF-36v2
- SDS
- TSQM
- H-DAT
- SIAQ-ISRQ

Assessments are to be performed according to [Table 2-1](#) and the assessment results from concomitant medication, vital signs and details of adverse events (AE) must be entered into the eCRF.

Investigator is to perform compliance check of treatment and reporting of bleeding episodes through reviewing collected data from the eDiary.

For patients not continuing in the prolongation of the trial a completion session must be made at Visit 16 in the IWRS. In the period from visit 16 to visit 17 the patient can be treated with turoctocog alfa at the discretion of the investigator. Turoctocog alfa may be requested via IWRS. Treatment can either be prophylactically and/or treatment of any bleeding episodes. Only

Protocol
 Trial ID:NN7415-4255
 UTN:U1111-1179-3872
 EudraCT no.:2016-000614-29

~~CONFIDENTIAL~~

Date: 28 August 2018
 Version: 5.0
 Status: Final
 Page: 52 of 127

Novo Nordisk

turoctocog alfa will be provided by Novo Nordisk. If necessary, a dispensing call must be performed in the IWRS. At the visit the patient will be provided with rFVIII (turoctocog alfa) and injection kits to be able to conduct home treatment until final visit.

For patients continuing in the prolongation of the trial and are enrolled in a subsequent trial a completion session must be made at visit 16 in the IWRS, but no additional trial product (turoctocog alfa) will be provided to the patient.

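### A prolongation patient whose visit 16 comes before visit 15.1 is not asked for the last PRO set, although section 8.6.1 wants it from all patients

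*Protocol*

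**What the plan says.** Section 8.6.1 sets the general rule for the last PRO assessment: "At visit 15.1 or 16 all patients should complete Hemo-TEM, SF-36v2, SDS, TSQM, H-DAT and SIAQ-ISRQ". Section 17.7.2 agrees, placing the last collection at either of these two visits.

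The flow chart footnotes in Table 2-2 are narrower.
- Footnote u: "PRO questionnaires should only be completed at 15.1 for patients continuing in the prolongation of the trial".
- Footnote v: "PRO questionnaires should only be completed at visit 16 for patients not continuing in the prolongation of the trial".

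The visit descriptions carry the same split. Section 8.1.10.2 asks only prolongation patients at visit 15.1, and section 8.1.10.3 asks only the others at visit 16, with the word 'not' in bold.

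On timing, section 8.1.10.3 schedules visit 16 on day 533 for patients who decline the prolongation, and on that day or later for those in the extension or entering a subsequent trial. Footnote s ends the repeat visits at roll-over: "Visit repeated every 8 week until patient either discontinues, completes extension or is enrolled into a subsequent trial with concizumab".

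On classification, section 8.1.10.3 describes three groups at visit 16: not in the prolongation; in the prolongation and entering a subsequent trial; in the prolongation but not entering one. The second begins: "For patients continuing in the prolongation of the trial and are enrolled in a subsequent trial a completion session must be made at visit 16".

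**The concern.** The restricted rule works only if every prolongation patient attends visit 15.1 before visit 16. Nothing in the protocol requires that order. Visit 16 becomes possible four weeks before visit 15.1 is due, and it is triggered by entry into the next trial or by stopping treatment.

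A patient who takes that route attends a full visit 16 but falls outside footnote v, and never has the visit 15.1 to which footnote u refers. The exploratory endpoints after at least 76 weeks (Hemo-TEM, SF-36v2, SDS, TSQM, SIAQ-ISRQ and H-DAT) then have no value for him. For H-DAT this is the only endpoint listed. Questionnaires that were not administered cannot be recovered by any later analysis rule. Roll-over is not a rare path either: section 5.2 expects most patients to join a subsequent trial.

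**Working it through.** **Schedule arithmetic.** The protocol's day numbering is day = 7 × week + 1.

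- Check on the plan's own figure: week 76 gives 7 × 76 + 1 = 533, the day stated for visit 16 in section 8.1.10.3.
- Visit 10 is on day 225, since 7 × 32 + 1 = 225 (section 8.1.10.1).
- From there, "Visits 11 to 15.n are to be scheduled with an interval of 8 weeks" (section 8.1.10.2), that is 56 days each. Visit 15 is five steps on: 225 + 5 × 56 = 505, week 72.
- Visit 15.1 is one further step: 505 + 56 = 561, week (561 − 1)/7 = 80.
- Gap between the earliest nominal visit 16 and visit 15.1: 561 − 533 = 28 days. With the ±7-day windows the outer limits are days 526 and 568.

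**Which rule applies to whom.**

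| Patient | Visit 15.1 | Visit 16 | PROs at week 76 or later |
|---|---|---|---|
| Declines the prolongation | none | day 533 | yes, at visit 16 |
| In the prolongation, reaches visit 15.1 | day 561 | later | yes, at visit 15.1 |
| In the prolongation, rolls over before visit 15.1 | none | about days 533 to 560 | none on the natural reading |
| In the prolongation, discontinues before visit 15.1 | none | visit 16 procedures (section 8.1.4) | none on the natural reading |

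In the first two rows section 8.6.1 and the footnotes agree. They part only in the last two.

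**What such a patient has on file.** By the visit list in section 8.6.1, visits 11 to 15 carry no questionnaires. His last Hemo-TEM, SF-36v2, SDS, TSQM and SIAQ-ISRQ are from visit 10 (day 225, week 32). His last H-DAT is from visit 9 (day 169, week 24).

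**How many.** Section 7 gives first treatment on 30-Aug-2017 and last patient first visit on 16-Dec-2017. Visit 2 follows visit 1 by 14 to 21 days, so I assume the last first dose fell between 30-Dec-2017 and 6-Jan-2018. Adding 532 days, day 533 falls between 13-Feb-2019 for the first patient and 15 to 22-Jun-2019 for the last. Adding 560 days, day 561 falls between 13-Mar-2019 and 13 to 20-Jul-2019. The number in the gap depends on when the subsequent trial opens and how fast patients enter it. The protocol gives neither. The only bounds are none and all 33 planned starters, which is no estimate.

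**The case against.** The best defence is that both rules can be met. The prolongation consists of the added visits 15.1 to 15.n. A patient who leaves at week 76 to 80 without attending any of them could be called not continuing in the prolongation, so his questionnaires fall at visit 16, as section 8.6.1 wants. The visit 16 scheduling rule lists extension patients and roll-over patients as alternatives, and footnote t speaks of entry into a subsequent trial without mentioning the prolongation. Section 8.1.10.3 also refers PRO completion back to section 8.6.1.

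This reading is possible, but it is nowhere stated and fits the text poorly. In section 8.1.10.3 roll-over patients appear only as prolongation patients. The not-continuing group is described as going on to visit 17 with turoctocog alfa available, whereas roll-over patients end the trial at visit 16. The introduction to Protocol Amendment 3 describes the intended path as added visits until a subsequent trial opens, then visit 16, with no condition that visit 15.1 comes first. What stands of the defence is that the conflict is confined to this one gap and turns partly on an undefined term.

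Three stronger readings are tempting. A reader might infer that sections 8.6.1 and 8.1.10.3 are irreconcilable throughout; they agree for everyone who declines the prolongation or reaches visit 15.1. A reader might work out a patient count by assuming even enrolment and one opening date; the documents support neither assumption, and such a snapshot would leave out patients who reach day 533 after that date. A reader might infer that losing patients who choose to stay on concizumab biases the remaining sample. Those who complete visit 15.1 have chosen the same, and who falls in the gap depends largely on calendar date and site participation. No link to PRO outcome is shown.

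**Conclusion.** The point holds for prolongation patients whose visit 16 precedes visit 15.1, by roll-over or discontinuation at about weeks 76 to 80. Followed as written, the plan does not ask these patients for the set that section 8.6.1 wants from all, and they have no value for the exploratory PRO endpoints after at least 76 weeks.

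This rests on two readings: that section 8.1.10.3 means what it says in describing roll-over patients as prolongation patients, and that no unstated rule puts visit 15.1 before visit 16. The number affected is unknown and no bias is demonstrated. The primary, secondary and safety endpoints and the 24-week PRO endpoints are untouched, and the later PRO changes are only to be described. It is a minor point, worth correcting because the loss is avoidable and cannot be repaired in analysis.

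**What to change.** Tie the visit 16 questionnaires to what has been completed, not to prolongation status. In footnote v of Table 2-2 and in section 8.1.10.3, write: *At visit 16 the PRO questionnaires are completed by every patient who has not completed them at visit 15.1.* Align footnote u and section 8.6.1 with the same rule. Patients who decline the prolongation, and those who complete the visit 15.1 set, keep their present schedule.

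The cost is one sentence in a few places and a change to the ePRO visit set-up. The visit and the questionnaires already exist, and no patient completes more than the one late set that section 8.6.1 already asks for.

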8.6.2 Training

The patients must be trained in how to handle bleeding episodes and how to recognize the signs and symptoms of thrombosis. The training must be recorded in the medical records.

8.6.2.1 Concizumab and NovoPen[®] 4

A direction for use (DFU) will be available as hand out for patients at visit 2. Training in NovoPen[®] 4 can start at screening (visit 1) and s.c. administration of concizumab using the NovoPen[®] 4 can start at the first dose at the trial site (visit 2). Patients must be instructed that injections are to be performed subcutaneously, not intravenously. Concizumab and NovoPen[®] 4 will be dispensed to patients at visit 2. Training must be performed at site until patients feel comfortable using the device or performing the treatment. The training must be documented in the medical records.

Detailed instructions can be found in the DFU.

